3. STUDY DESCRIPTION

3.1 Design

This is a randomized, double-blind (patients and physicians), placebo controlled multi-center study to evaluate the effect of ertugliflozin 5mg once daily (p.o.) for 52 weeks on the ventricular arrhythmic burden and markers of physical and mental well-being as well as biomarker for heart failure in HFrEF and HFmrEF patients with ICD±CRT therapy. The study will be conducted in 8 experienced sites in Austria with an aim to enrol 402 patients (Figure 1) to evaluate the overall study hypothesis.

[figure not shown]

Figure 1 Study Flow Chart

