7.1 Sample size and power considerations

Previous data showed that VT/VF episodes are decrease by two thirds within 6 months after initiation of sacubitril/valsartan in ICD±CRT patients (10). sVT/VF Episodes declined by 62.5% whereas nsVTs rate dropped by ~70%. Based on comparable effects on heart failure morbidity with either SGLT-2 inhibition or sacubitril/valsartan treatment we expect a profound reduction in sVT/VF in the treatment arm. Since data of the large SGLT2 outcome trials which did not focus on arrhythmias and their detection but only counted cases of sudden cardiac death have a signal of smaller effects we calculate with a decrease in the event rate of 30%. Moreover, the retrospective analysis by Martens et al provides a rather low event rate in their population. However, as pointed out in the Introduction other prospective randomized trials have considerably higher event rates. The sample size calculation is based on the mathematical formula provided by Zhu and Lakkis for comparing event rates of two negative binomial distributions (19). We used the function power.nb.test of the package MKmisc in R that implements the results of the paper cited above. According to that formula, the parameters needed to calculate the sample size are: The expected yearly rate of VT/VF episodes in the control group (r_0), The minimal clinical relevant effect (RR) defined here as the ratio of expected VT/VF episodes rates (RR = expected rate in treated/expected rate in control = r_1/r_0), the average follow-up or treatment duration (duration), the negative binomial dispersion parameter (k), the Type I error probability (α) and the power ($1 - \beta$). To detect a 30% reduction in VT/VF episodes rate in the ertugliflozin group as compared to the placebo group (i.e. using RR = 0.70), with a power of 80% and an alpha-level of 0.05%, a sample size of 191 patients in each group is needed. In this sample size calculation, we assumed the dispersion parameter k to be 1.0, the expected yearly rate of VT/VF episodes in the control group (i.e. r_0) to be 1.0 and an average follow-up of 11.4 months. To account for a dropout rate of about 5% in each group, we will need of 402 patients in each arm.

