7.2 Data analysis

Intention-to-treat (ITT) analyses will be applied as the primary analysis. Analysis of the primary endpoint is comparison of the number of sVT/VF episodes between treatment groups from randomization to week 52. The primary endpoint will be analysed using analysis of covariance (ANCOVA), with treatment as a fixed factor, the baseline number of sVT/VF episodes as a covariate and with adjustment for history of T2D and eGFR and site of randomization.

Normally distributed variables will be presented as mean \pm standard deviation (SD) and skewed distributed variables as median and interquartile range [IQR]. Comparisons between treatment and placebo group will be performed by an unpaired two sample *t*-test, Mann–Whitney test, or χ^2 test as appropriate.

A two-tailed p-value ≤ 0.05 will be considered statistically significant. A detailed statistical analysis plan including pre-specified subgroup analyses will be finalized ahead of database lock.

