## Ertugliflozin to Reduce Arrhythmic burden in ICD/CRT patientS (ERASE-Trial) – a phase III Study

on the mathematical formula provided by Zhu and Lakkis for comparing event rates of two negative binomial distributions (11). We used the function `power.nb.test` of the package `MKmisc` in R that implements the results of the paper cited above. According to that formula, the parameters needed to calculate the sample size are: The expected yearly rate of VT/VF episodes in the control group ( $r_0$ ), The minimal clinical relevant effect (RR) defined here as the ratio of expected VT/VF episodes rates (RR = expected rate in treated/expected rate in control =  $r_1/r_0$ ), the average follow-up or treatment duration (duration), the negative binomial dispersion parameter ( $k$ ), the Type I error probability ( $\alpha$ ) and the power ( $1 - \beta$ ). To detect a 30% reduction in VT/VF episodes rate in the ertugliflozin group as compared to the placebo group (i.e. using RR = 0.70), with a power of 80% and an alpha-level of 0.05%, a sample size of 191 patients in each group is needed. In this sample size calculation, we assumed the dispersion parameter  $k$  to be 1.0, the expected yearly rate of VT/VF episodes in the control group (i.e.  $r_0$ ) to be 1.3 and an average follow-up of 11.4 months. To account for a dropout rate of about 5% in each group, we will need of 402 patients in total.

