## **Ertugliflozin to Reduce Arrhythmic burden in ICD/CRT patientS (ERASe-Trial) – a phase III Study**

**RR =  $e^{\beta_1}$ .** The efficacy of the drug, compared to placebo, will then be investigated by testing the following null and alternative hypotheses:

$$H_0: \beta_1 = 0 \quad \text{vs.} \quad H_A: \beta_1 \neq 0$$

The function `glm.nb` from the MASS package in R will be used for this reason and for fitting the negative binomial regression model. The model will also adjust for the baseline number of sVT/VF. Sensitivity analysis will be carried out by using methods robust to outliers.

The analysis of secondary endpoints will be as follows: The number of incident nsVT, the number of appropriate ICD-treatment episodes, the total number of hospitalization due to heart failure will be analysed using a beta binomial model. The change in NTproBNP and the change in HbA1c levels from randomization to week 52 will be analysed using a multiple linear regression model. Hospitalization days from randomization to week 52 will be compared between the two groups using mean and SD. Cardiovascular mortality will be analysed by comparing proportions across the two groups.

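### Protocol 7.1 gives 402 patients per arm instead of in total, both documents print alpha as 0.05%, and once alpha is corrected to the planned two-sided 0.05 the stated 191 per group no longer gives 80% power

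*Protocol*

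**What the plan says.** **Sample size.** Protocol 7.1 arrives at 191 patients per group and closes with "To account for a dropout rate of about 5% in each group, we will need of 402 patients in each arm". The Protocol synopsis lists 402 patients for the trial, and Protocol 3.1 gives 402 as the enrolment aim across its eight sites. SAP 4 repeats the Protocol's sample-size paragraph but ends it differently: "we will need of 402 patients in total".

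**Alpha.** The sample-size paragraph in both documents reads "with a power of 80% and an alpha-level of 0.05%, a sample size of 191 patients in each group is needed". Protocol 7.2 sets the analysis level: "A two-tailed p-value ≤ 0.05 will be considered statistically significant". SAP 5 says that efficacy "will then be investigated by testing the following null and alternative hypotheses", and the hypotheses that follow are two-sided (coefficient equal to zero against not equal to zero). The SAP prints no other numerical significance level.

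**Other inputs.** Both documents use a rate ratio of 0.70, dispersion 1.0, average follow-up of 11.4 months, 80% power and about 5% dropout. The yearly control rate is 1.0 in Protocol 7.1 and 1.3 in SAP 4, yet both report 191 per group. Neither document states the sidedness or the null-variance option used in the calculation.

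**The concern.** The target size and the type I error are core design figures that a trial report reproduces. Taken literally, Protocol 7.1 doubles the target from 402 to 804. SAP 7 records early termination with a lower sample size, so planned and achieved numbers will have to be compared, and the size of the shortfall depends on which target is used.

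The alpha slip matters for another reason. Because 0.05% cannot be the level behind 191, the reader has to guess which level was. The natural guess, two-sided 5%, does not return 191 at either stated control rate. The misprint therefore hides a mismatch between the sample-size calculation and the planned two-sided test, and the claim of 80% power rests on that calculation.

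**Working it through.** **1. Dropout step.** Inputs: 191 per group and 5% dropout (Protocol 7.1, SAP 4).

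- Multiplying up: 191 × 1.05 = 200.55, so 201 per arm and 402 in total.
- Dividing by retention: 191 / 0.95 = 201.05. Across both arms this is 402.1, or 202 per arm (404 in total) if each arm is rounded up.
- For comparison, 402 / 191 = 2.10, so 402 per arm would be an inflation of about 110%, not 5%.

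The plan's 402 is therefore reproduced as a total.

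**2. Formula for 191.** Both documents cite the Zhu–Lakkis method for two negative binomial rates. With equal groups, control rate r0, rate ratio RR, follow-up t in years and dispersion k:

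- n per group = (z_α √V0 + z_β √V1)² / (ln RR)²
- V1 = (1/t)(1/r0 + 1/(RR·r0)) + 2k
- V0, pooled-rate option = 4 / (t·r0·(1 + RR)) + 2k

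Inputs: RR = 0.70, so (ln RR)² = 0.1272; k = 1.0; t = 11.4/12 = 0.95; z_β = 0.842.

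- r0 = 1.0 (Protocol): V1 = 4.556, V0 = 4.477, with roots 2.135 and 2.116.
- r0 = 1.3 (SAP): V1 = 3.966, V0 = 3.905, with roots 1.992 and 1.976.

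**3. Reproducing the plan's figure.** One-sided 5% with r0 = 1.3: (1.645 × 1.976 + 0.842 × 1.992)² / 0.1272 = 190.8, which rounds up to 191.

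**4. All combinations.** Patients per group for 80% power, pooled-rate option first. The brackets give the range over three null-variance options (control rate in both arms, unpooled, pooled).

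| Alpha | r0 = 1.0 (Protocol) | r0 = 1.3 (SAP) |
|---|---|---|
| 0.0005 two-sided | 660 (616–670) | 576 (542–583) |
| 0.0005 one-sided | 604 (564–612) | 526 (496–533) |
| 0.05 two-sided | 278 (262–282) | 243 (230–245) |
| 0.05 one-sided | 219 (207–222) | 191 (182–193) |

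No version of 0.05% comes near 191, and neither does two-sided 5% at either stated rate.

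**5. Power of 191 per group at the planned two-sided 0.05.** Power = Φ[(√n·|ln RR| − z_α √V0) / √V1], with √191 × 0.3567 = 4.929.

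- r0 = 1.3: (4.929 − 1.960 × 1.976) / 1.992 = 0.530, so 70%.
- r0 = 1.0: (4.929 − 1.960 × 2.116) / 2.135 = 0.367, so 64%.

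Over the three null-variance options the ranges are 70–73% and 64–67%.

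**6. Whether 402 per arm could have been meant.** With 5% dropout, 402 per arm leaves 402 × 0.95 ≈ 382 evaluable. At two-sided 0.05 that gives about 91% power (r0 = 1.0) or 94% (r0 = 1.3), so it is not an 80% design either.

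**The case against.** The strongest reply is that these are drafting slips which the documents resolve themselves. The synopsis, Protocol 3.1 and SAP 4 all give 402 for the trial, and 191 per group settles the meaning within the same paragraph of Protocol 7.1. The alpha in that paragraph is only an input to a sample-size formula. The level at which results are judged is set separately, and clearly, in Protocol 7.2. The trial has already stopped early, so neither wording can change enrolment.

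Most of this stands, and it rules out three stronger readings:

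- **That the trial tests at 0.0005.** A reader of the SAP alone might infer this, because 0.05% is the only level printed there. Protocol 7.2 says otherwise, no section plans a test at that level, and the value is incompatible with 191. Power computed at 0.0005 would describe a design that nobody proposed.
- **That the target was 804.** Only one phrase supports it, against three other statements and the paragraph's own arithmetic.
- **That more patients should have been enrolled.** The 243 and 278 per group measure the gap between the calculation and the test. They are not a new recruitment target for a trial that has ended.

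What the reply does not answer is the power claim. Correcting the two phrases to 402 in total and a two-sided 5% would leave 191 per group and 80% power beside an alpha that does not deliver them.

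**Conclusion.** The point holds. The phrase giving 402 per arm in Protocol 7.1 is wrong by a factor of two, and the 0.05% in both documents is wrong as printed. The decision rule of two-tailed 0.05 is stated correctly in Protocol 7.2 and is not in doubt.

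The substantive remainder is that 191 per group matches only a one-sided 5% calculation at a control rate of 1.3. For the two-sided test that is planned, the full design has about 70% power at that rate, or 64% at the Protocol's rate of 1.0, instead of 80%.

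These figures assume the stated rate ratio, dispersion and follow-up, equal groups, the pooled-rate null variance, and no gain from covariate adjustment beyond the stated dispersion. The other null-variance options move the power by about 3 percentage points at most. That the calculation was actually run one-sided is an inference from the match, not something the documents say. The figures describe the planned design. The documents do not give the number enrolled, so they say nothing about the power achieved.

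**What to change.** - **Protocol 7.1:** state 402 patients in total (201 per arm).
- **Protocol 7.1 and SAP 4:** replace 0.05% with the alpha and the sidedness actually used in the calculation.
- **Control rate:** reconcile 1.0 in the Protocol with 1.3 in the SAP, and say which one produced 191.
- **Power:** rerun the calculation at the two-sided 0.05 of Protocol 7.2 and print the resulting power beside 191 per group. A two-sided 5% should not simply be inserted next to 191 and 80%.
- **Reporting:** express any shortfall after early termination against 402 in total, and give the restated power with it.

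The cost is one rerun of the sample-size function and a few changed words and figures in one paragraph of each document. No additional patients, no new data and no change to the analysis are needed.

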7.2 Data analysis

Intention-to-treat (ITT) analyses will be applied as the primary analysis. Analysis of the primary endpoint is comparison of the number of sVT/VF episodes between treatment groups from randomization to week 52. The primary endpoint will be analysed using analysis of covariance (ANCOVA), with treatment as a fixed factor, the baseline number of sVT/VF episodes as a covariate and with adjustment for history of T2D and eGFR and site of randomization.

Normally distributed variables will be presented as mean \pm standard deviation (SD) and skewed distributed variables as median and interquartile range [IQR]. Comparisons between treatment and placebo group will be performed by an unpaired two sample *t*-test, Mann–Whitney test, or χ^2 test as appropriate.

A two-tailed p-value ≤ 0.05 will be considered statistically significant. A detailed statistical analysis plan including pre-specified subgroup analyses will be finalized ahead of database lock.

8. DATA MANAGEMENT

Data Management is the responsibility of the Medical University of Graz, Department of Cardiology and the study Monitor. The subject and the biological material obtained from the subject will be identified by subject number, trial site and trial identification number. Appropriate measures such as encryption or deletion will be enforced to protect the identity of human subjects in all presentations and publications as required by local/regional and national requirements.

This study will capture and process data using an electronic Case Report Form. Data and reports will be extracted from the database throughout the study to monitor progress and training will be provided to all study staff on use of the database. The study will be monitored by qualified employees of the research group of cardiovascular Diabetology based on a specific monitoring plan.

9. TREATMENT

9.1 Study medication

Ertugliflozin is a sodium-glucose cotransporter 2 (SGLT2)-inhibitor. It works by increasing the amount of sugar that leaves the body in the urine. The study dose is 5mg once daily in the morning, taken with or without food. Each tablet contains 5mg Ertugliflozin or Placebo. The pharmaceutical form is a 6.4 x 6.6 mm large triangular tablet debossed „701“ on one side. Ertugliflozin has minor influence on the ability to drive and use machines. Patients should be advised to take precautions to avoid hypoglycaemia while driving and using machines, in particular when Ertugliflozin is used in combination with a sulfonylurea and/or insulin. Pharmacy (Anstaltsapotheke) at the University Hospital of Graz, Austria will pack the medication as 52 weeks supplies for study participants and label study medication according to current regulatory requirements.

9.2 Method of administration

The tablets can be taken with or without food, swallowed whole with water. If a dose is missed, it should be taken as soon as the patient remembers. A double dose should not be taken on the same day.

9.3 Special precautions for storage

The study drug must be kept locked in a secure area. No particular storage conditions are required.

9.4 Dispensing of Study Drug

The study team shall dispense the study drug only to subjects entered into the study, under the direction of the PI or sub-investigators authorized to receive or dispense it. The study drugs will not be dispensed or supplied to any person not authorized to receive it. Each time a study drug is dispensed; there must be documentation in the sponsor provided log (drug accountability log) as to the amount dispensed, to whom it is dispensed, and the date and signature or initials of the person dispensing the drug. Subjects should be advised to follow the study protocol and as appropriate to protocol return all used and unused containers to the site at study visit 2 (week 52). Any discrepancies between the amounts used by the subjects and the amount returned should be documented.

9.5 Return/Destruction of Study Drug

Assure that unused supplies of the study drug are returned to the sponsor in accordance with sponsor requirements. Obtain authorization from the sponsor if unused supplies of the study drug will be disposed of at the end of the study. Maintain records of the return or disposition of the unused study drug, including the unused study drug amount, lot numbers and quantity, method of return or disposition, and any documentation related to shipment or destruction. At the end of the study ensure that all documentation regarding receipt, storage, dispensing, return of used containers, and accountability is complete and accurate.

10. REGULATORY, ETHICAL AND LEGAL ISSUES

10.1 Declaration of Helsinki

The investigator will ensure that this study is conducted in full conformity with the 1964 Declaration of Helsinki and all subsequent revisions.

10.2 Good Clinical Practice

The study will be conducted in accordance with the guidelines laid down by the International Conference on Harmonisation for Good Clinical Practice (ICH GCP E6 guidelines).

10.3 Independent Ethics Committee/ competent authority

10.3.1 Initial Approval

Prior to the enrolment of subjects, the Ethics Committee at the Medical University of Graz must provide written approval of the conduct of the study at named sites, the protocol and any amendments, the Patient Information Sheet and Consent Form, any other written information that will be provided to the subjects, any advertisements that will be used and details of any subject compensation.

10.3.2 Approval of Amendments

Proposed amendments to the protocol and aforementioned documents must be submitted to the Ethics Committee for approval as instructed by the Sponsor. Amendments requiring approval may be implemented only after a copy of the approval letter has been obtained.

Amendments that are intended to eliminate an apparent immediate hazard to subjects may be implemented prior to receiving Sponsor or the Ethics Committee approval. However, in this case, approval must be obtained as soon as possible after implementation.

10.3.3 Competent Authority

Clinical Trial Applications (EudraCT application and the documents required for the assessment) should be addressed to the Austrian Competent Authority, the Federal Office for Safety in Health Care (Bundesamt für Sicherheit im Gesundheitswesen, BASG) under the following address:

Austrian Federal Office for Safety in Health Care (BASG)
Austrian Agency for Health and Food Safety (AGES)
Institute Surveillance (INS), Department for Clinical Trials (CLTR)
[name]
[name]

10.4 Insurance

Participant insurance according to legal requirements will be contracted.

10.5 Informed Consent

The participation of a subject in this clinical trial is voluntary. The investigator or a member of the research team will approach the patient to obtain informed consent. The background of the proposed study, the procedure, the follow-up schedule and all potential benefits and risks will be carefully explained to each subject. The person obtaining the informed consent shall:

- Avoid any coercion or undue influence of subjects to participate
- Not waive or appear to waive subject's legal rights
- Use language that is non-technical and understandable to the subject
- Clarify the subject that his/her data are confidential and are encoded with a subject ID number during the investigation
- Provide plenty of time for the subject to consider his/her participation
- Include dated signatures of the subject and of the clinical investigator
- Ask whether the subject has any questions about the study

After a subject has received and read the patient information sheet and agrees to participate in the study, the informed consent form approved by the Ethics Committee must be signed by the subject prior to any study specific tests being performed. It will also be signed by the person responsible for collecting the informed consent. The original will be kept in the subjects study research notes (source documents), a copy will be given to the subject and a copy kept in their hospital notes.

10.6 Subject Confidentiality

The investigator must ensure that the subject's privacy is maintained. On the CRF or other documents submitted to the Sponsors, subjects will be identified by a subject ID number only. Documents that are not submitted to the Sponsor (e.g., signed informed consent form) should be kept in a strictly confidential file by the investigator. The investigator shall permit direct access to subjects' records and source document for the purposes of monitoring, auditing, or inspection by the Sponsor, authorised representatives of the Sponsor, Regulatory Authorities and Ethic Committees.

10.7 End of Trial

The trial will end after the last subject has completed the follow-up telephone assessment (Study visit 3). All patients will be reviewed by a clinician at their last study visit in order to arrange return to appropriate routine clinical care pathways.

10.8 Study Documentation and Data Storage

The investigator must retain essential documents until notified by the Sponsor, and at least for 15 years after study completion, as per the Sponsor's requirements. Subject files and other source data (including copies of protocols, CRFs, original reports of test results, correspondence, records of informed consent, and other documents pertaining to the conduct of the study) must be kept for the maximum period of time permitted by the institution. Documents should be stored in such a way that they can be accessed/data retrieved at a later date, either in paper or electronically. Consideration should be given to security and environmental risks.

No study document will be destroyed without prior written agreement between the Sponsor and the investigator.

